9.0 Conventions and Derivations

Variables reported with different units will be homogenized to standardized variables following the International System of Units (e.g. laboratory tests, biometrical assessments...) unless otherwise specified.

By default, all results will be rounded to one decimal place, except when variables are integer, which will be reported without decimals (e.g., age in years). Percentages for 0 counts will not be presented and 100% values will be presented with no decimal places. For representing p-values four decimals will be selected as default but they could be rounded to fewer decimals if necessary.

Missing values will not be included in the calculation of outputs. Unless otherwise noted, missing data will not be imputed or carried forward.

For patients who discontinue treatment due to adverse events (related or not to study treatment) every effort should be made to remain under study follow-up, anyway, if information is lost before day 28 the conservative value of death will be also imputed.

Patients with no available data for any time-to event efficacy endpoint will be censored at time 0. EOS: Day 60 (± 3) or date of early study termination, if applicable. Patients not yet achieving the time to event endpoint will be censored at the last valid assessment prior to EOS. Efron's method will be used to handle ties.

Assessment windows as specified in the clinical protocol will be respected, see protocol Appendix 13 'Schedule of Assessments and Procedures' for definitions of trial days. Baseline is defined as latest test performed between screening and drug administration.

Change from baseline (%) is defined as: $(\text{test value} - \text{baseline value}) / \text{baseline value} \times 100$.

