Percentage of patients receiving immune-modulating drugs on Days 1, 4 (± 1), 8 (± 1), 15 (± 1), 30 (± 2), and 60 (± 3).	-Frequencies	-FAS population
Time to onset of additional (i.e., not present at baseline) antiviral drugs.	-Kaplan-Meier (unstratified)	-FAS population

Endpoints	Analyses	Population
Percentage of patients receiving subsequent antiviral drugs (i.e., not present at baseline) on Days 4 (± 1), 8 (± 1), 15 (± 1), 30 (± 2), and 60 (± 3).	-Frequencies	-FAS population
Percentage of patients with a new infection by Days 4 (± 1), 8 (± 1), 15 (± 1), 30 (± 2), and 60 (± 3).	-Frequencies	-FAS population
Cumulative mortality (all-cause and related to COVID-19) by Days 4 (± 1), 8 (± 1), 15 (± 1), 30 (± 2), and 60 (± 3).	-Frequencies	-FAS population
Percentage of patients in each study group who require subsequent admission within 30 days of initial end of hospital care [up to day 60(± 3)], related to either COVID-19 or COVID-19 therapy.	-Frequencies	-FAS population
Change respect to Day 1 in the viral load of SARS-CoV-2, measured by RT-PCR, by Days 4 (± 1), 8 (± 1), 15 (± 1), 30 (± 2), and 60 (± 3), in each study group.	-Summary statistics	-FAS population
Percentage of patients in each study group with undetectable viral load, by Days 4 (± 1), 8 (± 1), 15 (± 1), 30 (± 2), and 60 (± 3).	-Frequencies	-FAS population
Time to either undetectable viral load of SARS-CoV-2 or > 2 logs reduction respect to Day 1.	-Kaplan-Meier (unstratified)	-FAS population
Change respect to baseline in inflammatory biomarkers (C-reactive protein [CRP], procalcitonin, lactate dehydrogenase [LDH], ferritin, neutrophil-to-lymphocyte ratio, and multiplex cytokines assay,	-Summary statistics	-FAS population

Endpoints	Analyses	Population
by Day 4 (± 1), 8 (± 1), 15 (± 1) and 30 (± 2) and 60 (± 3).		
Change respect to baseline in individual serological assessments against SARS-CoV-2, by Days 30 (± 2), and 60 (± 3).	-Summary statistics	-FAS population
Change respect to baseline in individual T-cell response against SARS-CoV-2 by Days 30 (± 2), and 60 (± 3).	-Summary statistics	-FAS population
Change respect to baseline to Days 15 (± 1), and 30 (± 2) in chest X-ray findings (Brixia score, centrally assessed) (Protocol Appendix 9 – Brixia Score).	-Summary statistics	-FAS population
Percentage of patients requiring modification of the therapy (drugs, dose or schedule) for the underlying disease.	-Frequencies	-FAS population

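### The SAP's only change-from-baseline formula is a percentage that is undefined at a zero baseline, and no other scale is named for the serology, T-cell, cytokine, Brixia and viral-load change endpoints

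*SAP*

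**What the plan says.** SAP 9.0 sets the derivation rules. Its one formula for change begins "Change from baseline (%) is defined as" and divides the difference by the baseline value. The reference value is also fixed there: "Baseline is defined as latest test performed between screening and drug administration". Two further conventions in that section matter: "Missing values will not be included in the calculation of outputs", with no imputation unless noted otherwise, and "By default, all results will be rounded to one decimal place". Nothing is said about a baseline that is zero or below a quantification limit.

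Table 3 in SAP 11.8 lists the endpoints concerned. Examples are "Change respect to baseline in individual serological assessments against SARS-CoV-2, by Days 30" and 60, "Change respect to baseline in individual T-cell response against SARS-CoV-2 by Days 30" and 60, and the Day 15 and Day 30 change "in chest X-ray findings (Brixia score, centrally assessed". Change in inflammatory biomarkers (including the cytokine panel) and in viral load from Day 1 is listed in the same way. For each, the planned analysis is summary statistics in the FAS, with no scale stated.

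Other parts of the SAP treat change differently. Section 11.7 uses shift tables for laboratory grades. Section 8.3 has a time-to-event endpoint with a threshold of more than 2 logs for viral load. Section 11.9 summarises changes in vital signs and chest imaging by visit, again without a scale.

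**The concern.** A programmer looking for a derivation rule for these endpoints finds only the percent formula. It fails at a zero baseline, is unstable just above zero, and suits viral load poorly. Low or zero baselines are plausible here. Group 2 receives B-cell depleting therapy, and Protocol 1.1 cites weaker vaccine response under anti-CD20 treatment. Entry requires a listed sign or symptom but not pneumonia (Protocol 4.1), so a clear film at entry is possible.

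Protocol 8.5 planned univariate tests and mixed models for these endpoints. SAP version 3.0 drops them after early closure, so the descriptive table is what remains. SAP 6.0 says such tables are meant to allow a numerical comparison of the arms. Leaving the scale open also leaves a choice to be made with the arms visible: SAP 8.2 records a decision on 19 March 2024 to unmask the data, and the SAP is dated 20 March 2024.

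**Working it through.** The plan gives no figure to reproduce on this point, so the check applies the SAP formula to assumed values.

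**Formulas.** Percent change P = (t - b) / b x 100 (SAP 9.0). Absolute change A = t - b. Here b is baseline and t the later value.

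**Step 1: zero and near-zero baselines.**

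| b | t | A | P |
|---|---|---|---|
| 0 | 0 | 0 | undefined |
| 0 | 6 | +6 | undefined |
| 1 | 6 | +5 | +500.0% |
| 6 | 12 | +6 | +100.0% |
| 12 | 6 | -6 | -50.0% |

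The smaller absolute rise (1 to 6) gives the larger percentage, and equal moves up and down (6 to 12, 12 to 6) do not mirror each other.

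**Step 2: effect of leaving out undefined values.** Take the planned 20 patients per arm (SAP 8.5). Assume that k of them have a zero baseline and rise from 0 to 8, and that the rest rise from 10 to 12. The mean of P uses only the rest: (12 - 10) / 10 x 100 = 20.0%, whatever k is. The mean of A uses all 20: (8k + 2(20 - k)) / 20.

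| Zero at baseline | Left out | Mean P | Mean A |
|---|---|---|---|
| 10% (k = 2) | 2 | +20.0% | (16 + 36)/20 = 2.6 |
| 30% (k = 6) | 6 | +20.0% | (48 + 28)/20 = 3.8 |
| 50% (k = 10) | 10 | +20.0% | (80 + 20)/20 = 5.0 |

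The shares are illustrative; the documents give no count.

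**Step 3: viral load.** On the raw scale, a fall of L log10 gives P = (10^(-L) - 1) x 100, printed to one decimal:

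- L = 2: -99.0%
- L = 3: -99.9%
- L = 3.25: -99.9%
- L = 4: -100.0%

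The value 3.25 is the mean log10 reduction by Day 15 that Protocol 1.2.1.3.1 reports for the earlier COVID-19 study. It cannot be told from 3, and a 4-log fall reads as complete clearance. If values are already held in log10, the formula fails in another way: a 3-log fall from 6 reads -3/6 = -50.0%, and the same fall from 5 reads -3/5 = -60.0%.

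**The case against.** The strongest reply is that SAP 9.0 defines one labelled quantity, a percent change, and does not say that every change endpoint is reported that way. Absolute change is plain subtraction and arguably needs no definition. Neither the Table 3 entries nor the protocol calls these changes percentages, and the SAP uses other scales elsewhere. That stands, so the exclusion and the compression are conditional on the formula being applied as written. It does not remove the gap, because on the other reading these endpoints have no stated scale at all.

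The harm is also softened. SAP 11.0 asks for medians and quartiles alongside means, for listings of all CRF variables, and for time-course figures including viral load. A median resists a few extreme percentages and listings keep individual responders visible, but neither puts excluded patients back into the summary. If a negative result is stored at a quantification limit and not as zero, nobody is lost, although the percentages then become very large. The documents do not say which applies.

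A reader might infer three stronger things that the documents do not support:

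- **That the patients lost are precisely those whose change matters.** For antibody and T-cell response, a patient at zero is one who could newly respond, but that patient is lost only if negatives are stored as zero. For the chest film the inference runs the wrong way: assuming that a clear film scores zero, such a patient can only stay clear or worsen, while those who can improve remain in.
- **That the SAP plans to report viral load as a percentage.** No section says so.
- **That the size of the loss can be read from vaccination status.** The compassionate-use series in Protocol section 1.2.1.3.3 covers 33 patients, 75.8% with at least one vaccine dose. Being unvaccinated is not the same as being seronegative in infected patients.

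**Conclusion.** The point holds in conditional form. The only change rule that the SAP writes out gives undefined, unstable or uninformative values for several named endpoints, and no alternative scale is stated for them. The conclusion about lost patients rests on three assumptions: that the formula is applied to these endpoints, that negative or clear results are stored as zero, and that undefined values are handled as missing. The number affected is unknown.

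The consequence is limited. These are other secondary or exploratory endpoints, reported descriptively with no formal tests. The primary mortality endpoint and the key secondary time to negativisation do not use a change from baseline. The point is still worth correcting, because the summary tables are now the planned basis for comparing the arms on these outcomes.

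**What to change.** In SAP 9.0, replace the single formula with a stated scale for each endpoint:

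- Absolute change (value minus baseline) for the Brixia score and vital signs.
- Log10 change for viral load and antibody titres.
- Absolute or log10 change for T-cell response and cytokines, with the choice written down.
- One fixed substitution for values below the quantification limit, used at baseline and at later visits alike.
- Percent change only for parameters that are strictly positive, with the number of patients excluded from any percent-change summary shown in the table.

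The proportion newly seropositive would be a useful optional addition, but it is a new summary and not a correction.

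The cost is one SAP paragraph, scale labels in Table 3 and changes to the derivation code. No new data are needed. Any affected tables already produced would have to be rerun.

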9.1 Imputation in Incomplete Dates

Dates of certain historical or current clinical activities are key component for statistical analysis. An incomplete date results from a missing day, month or year; in that case, the missing figure can be imputed allowing for the calculation of variables, such duration and time to certain event. However, when all of them, day, month and year, are missing no imputation will be done.

Before randomisation/treatment start date

All variables needed to summarize for example prior information where partial information is available will be subject of imputation by means of SAS programming. If the day of a date is unknown then the imputed day will be 1, if the month is also unknown then the imputed date will 1/July. This assumption will be valid if the imputed date is earlier than the randomisation date; otherwise, the imputed date will be the first day of the month of the randomisation date (i.e. 01/Randomisation month date/year).

Between treatment start and end of treatment

All date variables during treatment where information is needed and is not fully available, for example adverse events or concomitant medications, will be subject of imputation by means of SAS programming. If the day of a date is unknown then the imputed day will be 1, if the month and/or year is also unknown then the imputed date will be 1/January (this assumption will be valid if the imputed date is earlier than the treatment start date; otherwise, the imputed date will be the treatment start date). For treatment emergent AEs/CMs a conservative approach will be taken and if imputed date may be considered treatment emergent or medication taken on treatment then always will be counted.

After end of treatment

A conservative approach for the variables collecting information after end of treatment where partial information is available will be imputed by means of SAS programming. The following rules will be implemented: if the day of a date is unknown then the imputed day will be 1; if the month is also unknown, then the imputed date will be 1/July. This assumption will be valid if the imputed date occurs later than the last drug administration date; otherwise, the imputed date will be the last drug administration date plus 1 day.

10.0 Independent Data Monitoring Committee

An IDMC was established to provide study oversight. The IDMC was established and operated in compliance with the FDA Guidance for Industry "Establishment and Operation of Clinical Trial Data Monitoring Committees".

A separate IDMC charter has been written in order to specify the whole IDMC study conduct.

11.0 Statistical Methods

Non-continuous variables will be described in frequency tables using counts and percentages. Continuous variables will be described by median, mean, standard deviation (STD), interquartile range (Q1-Q3),

minimum and maximum. Study endpoints will be summarized by means of tables, listings for all CRF variables and figures for temporal series as viral load, lymphocytes/neutrophils evolution, LDH, CT>30 or oxygen necessities as well as Kaplan-Meier figures, as inverse KM (see section 11.8) where time to event data Y-axis started from 0% instead the usual 100%, e.g. time to confirmed negativisation in SARS-CoV-2 antigen test or RT-PCR Ct > 30, will be shown.

11.1 Subject disposition

Main characteristics concerning inclusion in the study, randomisation, enrolment by country/site, end of treatment and withdrawal of the study will be displayed in this section.

11.2 Demographic and Baseline Characteristics

Baseline data such as for example demographics, medical history, clinical evaluation will be described in the FAS population.

For pre-treatment characteristics with multiple measurements per patient before the start of treatment (e.g. laboratory assessments, vital signs), the baseline measurement will be considered the last value prior to or on the first day of treatment. Continuous variables that will be also presented as categorized summaries.

Age at informed consent will be summarized as continuous variable and categorized as <65y, >=65-74y and >=75y. Gender, race, stratification factors from eCRF randomization forms and from their corresponding eCRF forms, physical examination form including height, weight, BMI and abnormal results, respiratory assessments form including oxygen therapy status, SpO2, FiO2, SpO2/FiO2, PaO2 and PaO2/FiO2, vital signs form including systolic blood pressure, diastolic blood pressure, pulse and respiratory rate, ECG Test Results - Local Reading form including heart rate, PR interval, QRS duration, QT interval, QTcF interval (Fridericia's formula) and QTcF (ECG measurements will be taken in triplicates but average values will be shown by visit), SARS-CoV-2 Test, COVID 19 Vaccination, duration of the infection prior to study entry defined as time from currently COVID-19 episode diagnosis date to randomization as continuous variable and categorized as <5 days and >=5 days and any additional variable considered as clinically relevant.

11.3 Treatment Administration

Treatment compliance defined as the extent to which patients take medications as requested in the protocol will be measured as duration in days of antiviral exposure ((Last exposure date-First exposure date)+1), total number of infusions/doses administered, the number of infusions/doses where total amount was administered, the number of infusions/doses where total amount was not administered and the number of infusions interrupted will be listed and summarized using descriptive statistics where applicable.

11.4 Protocol Deviations

A protocol deviation is defined as any departure from what is described in the protocol of a clinical trial. The study specific Protocol Deviation Guidance Document defines all important protocol deviations.

The study team will conduct on-going reviews of the deviation data and document must be finalized prior to database lock.

Summaries of protocol deviations will be produced.

Deviations with no effects on the risk/benefit ratio of the clinical trial (such as minimal delays in assessments or visits) will be distinguished from those that might have an effect on this risk/benefit ratio.

Below examples of deviation's classification are listed.

████████████████████

Table 2 Important protocol deviations.

Category	Sub Category	Project Specific Protocol Deviation
Study Conduct/ Procedures	Inclusion/ Exclusion Criteria	Failure to complete or comply with inclusion/exclusion criteria
Study Conduct/ Procedures	Screening	Non-compliance with screening procedure protocol requirements to confirm eligibility of the patient
Study Conduct/ Procedures	Study Restrictions/ Withdrawal	Non-compliance with protocol restrictions (e.g. use of prohibited medication or prohibited treatment therapy)
Study Conduct/ Procedures	Dose Formulation/ Dose Administration	Administration Use of prohibited medication
Study Conduct/ Procedures	Dose Formulation/ Dose Administration	Incorrect study drug dose, frequency, timing or method of drug delivery (e.g. subject overdosed with study drug, incomplete study drug administered), incorrect volume of infusion
Study Conduct/ Procedures	Dose Formulation/ Dose Administration	Study drug dosing adjustments performed outside of Protocol

All-important protocol deviations leading to exclusion from any population occurring during the study will be reviewed and approved by Pharma Mar prior to database lock.

11.5 Concomitant medications and procedures

Concomitant medication [Anatomical Therapeutic Chemical – World Health Organization (ATC-WHO) coded by means of WHODrug dictionary] will be described. The number and percentages of patients using at least one medication will be displayed according ATC1/ATC2/ATC4/Term. Any unplanned diagnostic, therapeutic or surgical procedure performed during the study period must be recorded in the eCRF and coded by Medical Dictionary for Regulatory Activities (MedDRA).

Administration of all concomitant drugs received prior the first drug administration or by the patient during the study must be reported in the appropriate section of the eCRF along with dosage information, dates of administration and reasons for use. Additionally, any unplanned diagnostic, non-diagnostic procedure, therapeutic or surgical procedure performed during the study period must be recorded in the eCRF.

11.6 Efficacy Analyses

This is an exploratory basket study to adequately approach the potential heterogeneity of clinical conditions included under the concept of immune compromise. The study implements a Bayesian methodology taking into account the relative low frequency of the conditions under study, the relative absence of prospective data of the outcomes of COVID-19 for the study populations (most of the available data are retrospective and belong to the early waves of the pandemic, with different viral variants than nowadays), along with the changing medical practices in these settings. Under these premises, a Bayesian approach is more appropriate in terms of efficient decision-making process, and will provide novel information for future therapeutic development in these clinical conditions (4).

The trial will use a minimally-informative prior of $N(0, 1)$ to update the information provided by the trial data to produce a posterior distribution.

The resultant posterior distribution will serve as a starting point for further trials within this area, whether as a key part of any information data packs provided to experts ahead of an elicitation meeting, or directly as the informed prior or hypotheses for further trials (5) (6).

A calibrated Bayesian hierarchical model (CBHM) described by Chu and Yuan (1) was planned to analyse the data, allowing data to be analysed by group and results from each group be used to enrich the data of the other groups. The calibration of the model allows strong information sharing when the treatment effect is similar among baskets, and shrinks that sharing towards 0 as the treatment effect becomes more heterogeneous.

Given the early termination of the study and the low recruitment in cohorts 1 and 3, the enrichment of groups with information from the other treatment groups will not be possible. Therefore, no CBHM will be performed for the main analysis and the information of the different cohorts will be combined, if applicable, only for safety analysis. The primary endpoint: 1-month† all-cause mortality rate will be studied by means of descriptive mortality rate analysis.

Primary Endpoint

The difference between treatment and control arms in all-cause mortality at 30 days was foreseen to be examined using a Bayesian comparison of proportions within the calibrated Bayesian hierarchical model (CBHM) framework described by Chu and Yuan (1).

As each basket completes, they would have been evaluated for efficacy, with information gained being used to update the analyses of successive baskets.

Due to the premature study closure no Bayesian specific outputs or sensitivity analyses will be generated

Secondary Endpoints/Other Endpoints

Frequency tables will be prepared for categorical variables, and continuous variables will be described by means of summary tables, which will include the median, mean, standard deviation, interquartile range, minimum, and maximum of each variable.

Frequentist methods will be calculated. Counts and percentages, with their corresponding exact confidence intervals, will be calculated for the binomial endpoints.

Time-to-event variables (e.g. key secondary endpoint) and their set time estimates will be defined as time from randomization to their corresponding event + 1 (see 8.3 section) and analysed according to the Kaplan-Meier method.

Key secondary endpoint, time to confirmed negativisation in SARS-CoV-2 antigen test or RT-PCR Ct > 30, will be analysed according to the Kaplan-Meier method.

<NOTE: Due to the premature study closure no complex specific outputs or sensitivity analyses will be generated>.

